7.1. Descriptive Analysis

Continuous endpoints will be summarized using means, standard deviation, medians, and interquartile ranges. The differences among groups will be compared using Kruskal-Wallis's test. Categorical endpoints will be summarized using frequency and proportion. Chi-square tests will be used to compare categorical endpoints. Point estimates with two-sided 95% confidence intervals will be produced for group differences. These endpoints, baseline covariate, and stratification factors used during randomization will be summarized by treatment intervention

for the ITT population. Similar analyses will be conducted for the PP population and safety population.

Alberta Health

7.2. Primary, secondary, and safety analyses

The linear regression model will be used to model the mean differences in the range of motion as a function of the intervention received. The unadjusted model will use a univariate linear regression model to assess whether the participants' means of range of motion received Ketotifen Fumarate (2 mg or 5 mg) differed from those who received lactose placebo. A multivariate regression model will be used to adjust for the effect of baseline covariates, i.e., sex, age, side of injury is the same as the dominant hand, type of elbow injury, concurrent injury and site as a random variable. Type of elbow injury is defined as AO/OTA classification, i.e., distal humerus vs. proximal radius and ulna. Table 2 summarizes the statistical analyses.

Table 2: Statistical Analysis of Primary, Secondary, and Safety Endpoints

| Study Endpoint | Statistical Model | Estimate of treatment effects |
|--|--|---|
| | | |
| The mean difference between | Linear regression | The unadjusted mean difference |
| injured and contralateral elbow | This model will be used to obtain the unadjusted mean | and the corresponding 95% |
| flexion-extension at Week 12 | difference between the injured and contralateral elbow | confidence intervals |
| | flexion-extension at Week 12. | |
| | Secondary | |
| The mean difference between injured and contralateral flexion at Week 12 | The data will be analyzed with or without adjusting for specific baseline covariates. The statistical models are described below: a) Linear regression model This model will be used to obtain the unadjusted mean difference between injured and contralateral flexion at Week 12. b) The mixed-effects linear regression model This model will be used to obtain the adjusted mean difference between injured and contralateral flexion at Week 12. b) The mixed effects linear regression model This model will be used to obtain the adjusted mean difference between injured and contralateral flexion at Week 12. The baseline covariates sex, age, side of injury is the same as the dominant hand, type of elbow injury, and concurrent injury will be regarded as fixed variables, and site as a random variable. Type of elbow injury is defined as AO/OTA classification, i.e., distal humerus vs. proximal radius and ulna. | The mean difference and its corresponding 95% confidence intervals for both the unadjusted and adjusted analysis |

Alberta Health Services

| Study Endpoint | Statistical Model | Estimate of treatment effects |
|---------------------------------|--|-----------------------------------|
| The mean difference between | The data will be analyzed with or without adjusting for | The mean difference and its |
| injured and contralateral elbow | specific baseline covariates. The statistical models are | corresponding 95% confidence |
| extension at Week 12 | described below: | intervals for both the unadjusted |
| | a) Linear regression model | and adjusted analysis |
| | This model will be used to obtain the unadjusted mean | |
| | difference between injured and contralateral extension | |
| | at Week 12. | |
| | b) The mixed-effects linear rearession model | |
| | This model will be used to obtain the adjusted mean | |
| | difference between injured and contralateral extension | |
| | at Week 12. The baseline covariates sex, age, side of | |
| | injury is the same as the dominant hand, type of elbow | |
| | injury, and concurrent injury will be regarded as fixed | |
| | variables, and site as a random variable. Type of elbow | |
| | injury is defined as AO/OTA classification, i.e., distal | |
| | humerus vs. proximal radius and ulna. | |
| The mean difference between | The data will be analyzed with or without adjusting for | The mean difference and its |
| Injured and contralateral elbow | specific baseline covariates. The statistical models are | corresponding 95% confidence |
| pronation at week 12 | a) Linear regression model | and adjusted analysis |
| | This model will be used to obtain the unadjusted mean | |
| | difference between injured and contralateral pronation | |
| | at Week 12. | |
| | | |
| | b) The mixed-effects linear regression model | |
| | This model will be used to obtain the adjusted mean | |
| | difference between injured and contralateral pronation | |
| | at Week 12. The baseline covariates sex, age, side of | |

| Study Endpoint | Statistical Model | Estimate of treatment effects |
|---|--|---|
| | injury is the same as the dominant hand, type of elbow injury, and concurrent injury will be regarded as fixed variables, and site as a random variable. Type of elbow injury is defined as AO/OTA classification, i.e., distal humerus vs. proximal radius and ulna. | |
| The mean difference between injured and contralateral elbow supination at Week 12 | The data will be analyzed with or without adjusting for specific baseline covariates. The statistical models are described below: a) Linear regression model This model will be used to obtain the unadjusted mean difference between injured and contralateral supination at Week 12. b) The mixed-effects linear regression model This model will be used to obtain the adjusted mean difference between injured and contralateral supination at Week 12. b) The mixed-effects linear regression model This model will be used to obtain the adjusted mean difference between injured and contralateral supination at Week 12. The baseline covariates sex, age, side of injury is the same as the dominant hand, type of elbow injury, and concurrent injury will be regarded as fixed variables, and site as a random variable. Type of elbow injury is defined as AO/OTA classification, i.e., distal humerus vs. proximal radius and ulna. | The mean difference and its corresponding 95% confidence intervals for both the unadjusted and adjusted analysis |

| Study Endpoint | Statistical Model | Es | timate of treatment effects |
|-------------------------------|--|----|---|
| The mean change in flexion- | The data will be analyzed using | • | ANCOVA: The p-value. |
| extension arc of the injuired | a) Analysis of Covariance (ANCOVA) | | |
| elbow from Week 2 to Week 52 | This model will be used to assess the mean difference in flexion-extension arc between Week 2 and Week 52 among the treatment groups after adjusting for flexion-extension arc at Week 2 (baseline value). The model will have Dependent variable: The flexion-extension arc at Week 52 Independent variable: Treatment group Covariate: Flexion-extension arc at Week 2, sex, age, side of injury is the same as the dominant hand, type of elbow injury, and concurrent injury will be regarded as fixed variables, and site as a random variable. Type of elbow injury is defined as AO/OTA classification, i.e., distal humerus vs. proximal radius and ulna. | - | Mixed-effect linear regression model: The mean difference and its corresponding 95% confidence intervals |
| | b) Mixed-effects linear regression model This model will be used to account for correlation among observations and estimate the effect of covariates on repeated outcomes. It will use the flexion- extension arc recorded at all time points. Also, the baseline covariates sex, age, side of injury is the same as the dominant hand, type of elbow injury, and concurrent injury will be regarded as fixed variables, and site as a random variable. Type of elbow injury is defined as AO/OTA classification, i.e., distal humerus vs. proximal radius and ulna. | | |

| Study Endpoint | Statistical Model | Estimate of treatment effects |
|--------------------------------|--|--|
| The mean change in flexion of | The data will be analyzed using | ANCOVA: The p-value. |
| the injuired elbow from Week 2 | a) Analysis of Covariance (ANCOVA) | |
| to Week 52 | This model will be used to assess the mean difference in flexion arc between Week 2 and Week 52 among the treatment groups after adjusting for flexion arc at Week 2 (baseline value). The model will have Dependent variable: The flexion arc at Week 52 Independent variable: Treatment group Covariate: Flexion arc at Week 2, sex, age, side of injury is the same as the dominant hand, type of elbow injury, and concurrent injury will be regarded as fixed variables, and site as a random variable. Type of elbow injury is defined as AO/OTA classification, i.e., distal humerus vs. proximal radius and ulna. | Mixed-effect linear regression model: The mean difference and its corresponding 95% confidence intervals |
| | b) Mixed-effects linear regression model This model will be used to account for correlation among observations and estimate the effect of covariates on repeated outcomes. It will use the flexion arc recorded at all time points. Also, the baseline covariates sex, age, side of injury is the same as the dominant hand, type of elbow injury, and concurrent injury will be regarded as fixed variables, and site as a random variable. Type of elbow injury is defined as AO/OTA classification, i.e., distal humerus vs. proximal radius and ulna. | |

| Study Endpoint | Statistical Model | Estimate of treatment effects |
|---|---|--|
| The mean change in extension arc of the injuired elbow from Week 2 to Week 52 | The data will be analyzed using Analysis of Covariance (ANCOVA) This model will be used to assess the mean difference in extension arc between Week 2 and Week 52 among the treatment groups after adjusting for extension arc at Week 2 (baseline value). The model will have Dependent variable: The extension at Week 52 | ANCOVA: The p-value. Mixed-effect linear regression model: The mean difference and its corresponding 95% confidence intervals |
| | Independent variable: Treatment group Covariate: Extension arc at Week 2, sex, age, side of injury is the same as the dominant hand, type of elbow injury, and concurrent injury will be regarded as fixed variables, and site as a random variable. Type of elbow injury is defined as AO/OTA classification, i.e., distal humerus vs. proximal radius and ulna. | |
| | b) Mixed-effects linear regression model This model will be used to account for correlation among observations and estimate the effect of covariates on repeated outcomes. It will use the extension arc recorded at all time points. Also, the baseline covariates sex, age, side of injury is the same as the dominant hand, type of elbow injury, and concurrent injury will be regarded as fixed variables, and site as a random variable. Type of elbow injury is defined as AO/OTA classification, i.e., distal humerus vs. proximal radius and ulna. | |

| Study Endpoint | Statistical Model | Estimate of treatment effects |
|---|--|--|
| The mean change in pronation of the injuired elbow from Week 2 to Week 52 | The data will be analyzed using a) Analysis of Covariance (ANCOVA) This model will be used to assess the mean difference in pronation between Week 2 and Week 52 among the treatment groups after adjusting for pronation arc at Week 2 (baseline value). The model will have | ANCOVA: The p-value. Mixed-effect linear regression model: The mean difference and its corresponding 95% confidence intervals |
| | Dependent variable: The pronation at Week 52 Independent variable: Treatment group Covariate: pronation at Week 2, sex, age, side of injury is the same as the dominant hand, type of elbow injury, and concurrent injury will be regarded as fixed variables, and site as a random variable. Type of elbow injury is defined as AO/OTA classification, i.e., distal humerus vs. proximal radius and ulna. | |
| | b) Mixed-effects linear regression model This model will be used to account for correlation among observations and estimate the effect of covariates on repeated outcomes. It will use the pronation recorded at all time points. Also, the baseline covariates sex, age, side of injury is the same as the dominant hand, type of elbow injury, and concurrent injury will be regarded as fixed variables, and site as a random variable. Type of elbow injury is defined as AO/OTA classification, i.e., distal humerus vs. proximal radius and ulna. | |

| Study Endpoint | Statistical Model | Estimate of treatment effects |
|--|--|--|
| The mean change in supination of the injuired elbow from Week 2 to Week 52 | The data will be analyzed using a) Analysis of Covariance (ANCOVA) This model will be used to assess the mean difference in supination between Week 2 and Week 52 among the treatment groups after adjusting for supination at Week 2 (baseline value). The model will have | ANCOVA: The p-value. Mixed-effect linear regression model: The mean difference and its corresponding 95% confidence intervals |
| | Dependent variable: The supination at Week 52 Independent variable: Treatment group Covariate: Supination arc at Week 2, sex, age, side of injury is the same as the dominant hand, type of elbow injury, and concurrent injury will be regarded as fixed variables, and site as a random variable. Type of elbow injury is defined as AO/OTA classification, i.e., distal humerus vs. proximal radius and ulna. | |
| | b) Mixed-effects linear regression model This model will be used to account for correlation among observations and estimate the effect of covariates on repeated outcomes. It will use the flexion- extension arc recorded at all time points. Also, the baseline covariates sex, age, side of injury is the same as the dominant hand, type of elbow injury, and concurrent injury will be regarded as fixed variables, and site as a random variable. Type of elbow injury is defined as AO/OTA classification, i.e., distal humerus vs. proximal radius and ulna. | |

| Study Endpoint | Statistical Model | Estimate of treatment effects |
|--|---|--|
| The mean difference in DASH score at Week 12 | The data will be analyzed with or without adjusting for specific baseline covariates. The statistical models are described below: a) Linear regression model This model will be used to obtain the unadjusted mean difference in DASH score at Week 12. | The mean difference and its corresponding 95% confidence intervals for both the unadjusted and adjusted analysis |
| | b) The mixed-effects linear regression model This model will be used to obtain the adjusted mean difference in DASH score at Week 12. The baseline covariates sex, age, side of injury is the same as the dominant hand, type of elbow injury, and concurrent injury will be regarded as fixed variables, and site as a random variable. Type of elbow injury is defined as AO/OTA classification, i.e., distal humerus vs. proximal radius and ulna. | |

| Study Endpoint | Statistical Model | Estimate of treatment effects |
|---|--|--|
| The mean difference in PCS score at Week 12 | The data will be analyzed with or without adjusting for specific baseline covariates. The statistical models are described below: a) Linear regression model This model will be used to obtain the unadjusted mean difference in PCS score at Week 12. | The mean difference and its corresponding 95% confidence intervals for both the unadjusted and adjusted analysis |
| | b) The mixed-effects linear regression model This model will be used to obtain the adjusted mean difference in PCS score at Week 12. The baseline covariates sex, age, side of injury is the same as the dominant hand, type of elbow injury, and concurrent injury will be regarded as fixed variables, and site as a random variable. Type of elbow injury is defined as AO/OTA classification, i.e., distal humerus vs. proximal radius and ulna. | |

| Study Endpoint | Statistical Model | Estimate of treatment effects |
|---|--|--|
| The mean difference in OES score at Week 12 | The data will be analyzed with or without adjusting for specific baseline covariates. The statistical models are described below: a) Linear regression model This model will be used to obtain the unadjusted mean difference in OES score at Week 12. | The mean difference and its corresponding 95% confidence intervals for both the unadjusted and adjusted analysis |
| | b) The mixed-effects linear regression model This model will be used to obtain the adjusted mean difference in OES score at Week 12. The baseline covariates sex, age, side of injury is the same as the dominant hand, type of elbow injury, and concurrent injury will be regarded as fixed variables, and site as a random variable. Type of elbow injury is defined as AO/OTA classification, i.e., distal humerus vs. proximal radius and ulna. | |

| Study Endpoint | Statistical Model | Estimate of treatment effects |
|---|--|--|
| The mean change in DASH score from Week 2 to Week 52 | The data will be analyzed using a) Analysis of Covariance (ANCOVA) This model will be used to assess the mean difference in DASH score between Week 2 and Week 52 among the treatment groups after adjusting for DASH score at Week 2 (baseline value). The model will have | ANCOVA: The p-value. Mixed-effect linear regression model: The mean difference and its corresponding 95% confidence intervals |
| | Dependent variable: The DASH score at Week 52 Independent variable: Treatment group Covariate: DASH score at Week 2, sex, age, side of injury is the same as the dominant hand, type of elbow injury, and concurrent injury will be regarded as fixed variables, and site as a random variable. Type of elbow injury is defined as AO/OTA classification, i.e., distal humerus vs. proximal radius and ulna. | |
| | b) Mixed-effects linear regression model This model will be used to account for correlation among observations and estimate the effect of covariates on repeated outcomes. It will use the DASH score recorded at all time points. Also, the baseline covariates sex, age, side of injury is the same as the dominant hand, type of elbow injury, and concurrent injury will be regarded as fixed variables, and site as a random variable. Type of elbow injury is defined as AO/OTA classification, i.e., distal humerus vs. proximal radius and ulna. | |

| Study Endpoint | Statistical Model | Estimate of treatment effects |
|--|---|--|
| The mean change in PCS score from Week 2 to Week 52 | The data will be analyzed using a) Analysis of Covariance (ANCOVA) This model will be used to assess the mean difference in PCS score between Week 2 and Week 52 among the treatment groups after adjusting for PCS score at Week 2 (baseline value). The model will have Dependent variable: The PCS score at Week 52 | ANCOVA: The p-value. Mixed-effect linear regression model: The mean difference and its corresponding 95% confidence intervals |
| | Independent variable: Treatment group Covariate: PCS score at Week 2, sex, age, side of injury is the same as the dominant hand, type of elbow injury, and concurrent injury will be regarded as fixed variables, and site as a random variable. Type of elbow injury is defined as AO/OTA classification, i.e., distal humerus vs. proximal radius and ulna. | |
| | b) Mixed-effects linear regression model This model will be used to account for correlation among observations and estimate the effect of covariates on repeated outcomes. It will use the PCS score recorded at all time points. Also, the baseline covariates sex, age, side of injury is the same as the dominant hand, type of elbow injury, and concurrent injury will be regarded as fixed variables, and site as a random variable. Type of elbow injury is defined as AO/OTA classification, i.e., distal humerus vs. proximal radius and ulna. | |

| Study Endpoint | Statistical Model | Estimate of treatment effects |
|------------------------------|--|--|
| The mean change in OES score | The data will be analyzed using | ANCOVA: The p-value. |
| from Week 2 to Week 52 | a) Analysis of Covariance (ANCOVA) | |
| from Week 2 to Week 52 | a) Analysis of Covariance (ANCOVA) This model will be used to assess the mean difference in OES score between Week 2 and Week 52 among the treatment groups after adjusting for OES score at Week 2 (baseline value). The model will have Dependent variable: The OES score at Week 52 Independent variable: Treatment group Covariate: OES score at Week 2, sex, age, side of injury is the same as the dominant hand, type of elbow injury, and concurrent injury will be regarded as fixed variables, and site as a random variable. Type of elbow injury is defined as AO/OTA classification, i.e., distal humerus vs. proximal radius and ulna. b) Mixed-effects linear regression model This model will be used to account for correlation among observations and estimate the effect of covariates on repeated outcomes. It will use the OES score recorded at the time points. Also, the baseline covariates sex, age, side of injury is the same as the dominant hand, type of elbow injury, and concurrent injury will be regarded as fixed variables, and site as a random variable. Type of elbow injury is defined as | Mixed-effect linear regression model: The mean difference and its corresponding 95% confidence intervals |
| | injury will be regarded as fixed variables, and site as a random variable. Type of elbow injury is defined as AO/OTA classification, i.e., distal humerus vs. proximal radius and ulna. | |

| Study Endpoint | Statistical Model | Estimate of treatment effects |
|---|---|--|
| | Safety | |
| Suspected unexpected Serious Adverse Reaction (SUSAR) up to Week 12 | The analyses will be unadjusted to avoid estimates with wide confidence intervals since we expected that the event rate might be low and that this is likely no event in some treatment groups. | Odds ratio and p-value for both the omnibus and pairwise differences models. |
| | Fisher's exact test The test will be used to compare the proportion of SUSAR up to Week 12 in the treatment groups. If the test produces a significant p-value at α = 0.05, a post-hoc test will be performed to identify groups that | |
| | differ. The p-values will be corrected using the Benjamin- Hochberg FDR method to ensure that the family-wise Type I error remains at 0.05. | |
| Fatal or life-threatening SAE up to Week 12 | The analyses will be unadjusted to avoid estimates with wide confidence intervals since we expected that the event rate might be low and that this is likely no event in some treatment groups. | Odds ratio and p-value for both the omnibus and pairwise differences models. |
| | Fisher's exact test The test will compare the proportion of Fatal or life- threatening SAEs in the treatment groups up to Week 12. | |

| Study Endpoint | Statistical Model | Estimate of treatment effects |
|---|--|--|
| | If the test produces a significant p-value at α = 0.05, a post-hoc test will be performed to identify groups that differ. | |
| | The p-values will be corrected using the Benjamin- Hochberg FDR method to ensure that the family-wise Type I error remains at 0.05. | |
| Other Serious adverse effect (SAE) up to Week 12 | The analyses will be unadjusted to avoid estimates with wide confidence intervals since we expected that the event rate might be low and that this is likely no event in some treatment groups. | Odds ratio and p-value for both the omnibus and pairwise differences models. |
| | Fisher's exact test The test will compare the proportion of other SAE in the treatment groups up to Week 12. | |
| | If the test produces a significant p-value at α = 0.05, a post-hoc test will be performed to identify groups that differ. | |
| | The p-values will be corrected using the Benjamin- Hochberg FDR method to ensure that the family-wise Type I error remains at 0.05. | |
| Composite reoperation for all elbow-related causes at Week 12 | The analyses will be unadjusted to avoid estimates with wide confidence intervals since we expected that the event rate might be low and that this is likely no event in some treatment groups. | Odds ratio and p-value for both the omnibus and pairwise differences models. |
| | Fisher's exact test | |

| Study Endpoint | Statistical Model | Estimate of treatment effects |
|--------------------------------|---|---------------------------------|
| | The test will compare the proportion of composite reoperation for all elbow-related causes in the treatment groups at Week 12. If the test produces a significant p-value at α = 0.05, a post-hoc test will be performed to identify groups that differ. | |
| | The p-values will be corrected using the Benjamin- Hochberg FDR method to ensure that the family-wise Type I error remains at 0.05. | |
| Participants requiring | The analyses will be unadjusted to avoid estimates with | Odds ratio and p-value for both |
| reoperation for contracture at | wide confidence intervals since we expected that the event | the omnibus and pairwise |
| Week 12 | rate might be low and that this is likely no event in some treatment groups. | differences models. |
| | Fisher's exact test | |
| | The test will compare the proportion of participants requiring reoperation for contracture at Week 12 in the treatment groups. | |
| | If the test produces a significant p-value at α = 0.05, a post-hoc test will be performed to identify groups that differ. | |
| | The p-values will be corrected using the Benjamin- | |
| | Hochberg FDR method to ensure that the family-wise | |
| | Type I error remains at 0.05. | |

| Study Endpoint | Statistical Model | Estimate of treatment effects |
|--|--|--|
| Suspected unexpected Serious | The analyses will be unadjusted to avoid estimates with | Odds ratio and p-value for both |
| Adverse Reaction (SUSAR) up to | wide confidence intervals since we expected that the event | the omnibus and pairwise |
| Week 52 | rate might be low and that this is likely no event in some | differences models. |
| | treatment groups. | |
| | Fisher's exact test The test will compare the proportion of SUSAR up to Week 52 in the treatment groups. | |
| | If the test produces a significant p-value at α = 0.05, a post-hoc test will be performed to identify groups that differ. | |
| | The p-values will be corrected using the Benjamin- Hochberg FDR method to ensure that the family-wise Type I error remains at 0.05. | |
| Fatal or life-threatening SAE up to Week 52 | The analyses will be unadjusted to avoid estimates with wide confidence intervals since we expected that the event rate might be low and that this is likely no event in some treatment groups. | Odds ratio and p-value for both the omnibus and pairwise differences models. |
| | Fisher's exact test | |
| | The test will compare the fatal or life-threatening | |
| | SAE proportion in the treatment groups up to Week 52. | |
| | If the test produces a significant p-value at α = 0.05, a post-hoc test will be performed to identify groups that differ. | |

| Study Endpoint | Statistical Model | Estimate of treatment effects |
|---|---|--|
| | The p-values will be corrected using the Benjamin- Hochberg FDR method to ensure that the family-wise Type I error remains at 0.05. | |
| Other Serious adverse effect (SAE) up to Week 52 | The analyses will be unadjusted to avoid estimates with wide confidence intervals since we expected that the event rate might be low and that this is likely no event in some treatment groups. Fisher's exact test: The test will compare the proportion of SAE up to Week 52 in the treatment groups. If the test produces a significant p-value at α = 0.05, a post-hoc test will be performed to identify groups that differ. The p-values will be corrected using the Benjamin-Hochberg FDR method to ensure that the family-wise | Odds ratio and p-value for both the omnibus and pairwise differences models. |
| Composite reoperation for all | The analyses will be unadjusted to avoid estimates with | Odds ratio and p-value for both |
| elbow-related causes at Week 52 | wide confidence intervals since we expected that the event rate might be low and that this is likely no event in some treatment groups. | the omnibus and pairwise differences models. |
| | Fisher's exact test | |
| | The test will compare the proportion of composite reoperation for all elbow-related causes in the treatment groups at Week 52. | |

Page 32 of 37

| Study Endpoint | Statistical Model | Estimate of treatment effects |
|---|---|--|
| | If the test produces a significant p-value at α = 0.05, a post-hoc test will be performed to identify groups that differ. The p-values will be corrected using the Benjamin-Hochborg EDB method to onsure that the family wise | |
| | Type I error remains at 0.05. | |
| Participants requiring reoperation for contracture at Week 52 | The analyses will be unadjusted to avoid estimates with wide confidence intervals since we expected that the event rate might be low and that this is likely no event in some treatment groups. | Odds ratio and p-value for both the omnibus and pairwise differences models. |
| | Fisher's exact test The test will compare the proportion of participants requiring reoperation for contracture in the treatment groups at Week 52. | |
| | If the test produces a significant p-value at α = 0.05, a post-hoc test will be performed to identify groups that differ. | |
| | The p-values will be corrected using the Benjamin- Hochberg FDR method to ensure that the family-wise Type I error remains at 0.05. | |

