| Study Objectives | Endpoints |
|------------------|---|
| | i. The Disability of the Arm, Shoulder, and Hand |
| | (DASH) |
| | ii. The Pain Catastrophizing Scale (PCS)) |
| | iii. The Oxford Elbow Score (OES) |
| 5. Safety | The proportion of SUSAR up till week 12 |
| | The proportion of fatal or life-threatening SAE up till week 12 |
| | The proportion of other SAE up till week 12 |
| | The proportion of composite reoperation for all elbow-related causes at week 12 |
| | The proportion of participants requiring reoperation for contracture at week 12 |
| | The proportion of SUSAR up till week 52 |
| | The proportion of fatal or life-threatening SAE up till week 52 |
| | The proportion of other SAE up till week 52 |
| | The proportion of composite reoperation for all elbow-related causes at week 52 |
| | The proportion of participants requiring reoperation for contracture at week 52 |

6. Analysis Set

a) Intent-to-Treat (ITT) Population: The primary endpoint analysis will be conducted on the ITT population, which includes all study participants and the treatment group to which they were assigned (i.e., the intended treatment). An ITT analysis will also be conducted for the secondary endpoints.

Alberta Health

- b) **Per Protocol (PP) Population:** The PP population includes all participants randomized and treated, with no major protocol deviations, including not meeting inclusion/exclusion criteria, not receiving the planned dose, receiving the incorrect study drug, or not obtaining consent (i.e., as treated). The primary analysis will be repeated on the PP population.
- c) **Safety Population:** The safety population comprises all participants receiving any amount of study drug. Participants will be analyzed based on the intervention they receive.

7. Statistical Analysis

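### SAP Section 7.2 describes the range-of-motion model by intervention received, which contradicts the rule in Section 6(a) that these endpoints are analysed by assigned arm

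*SAP*

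**What the plan says.** SAP Section 6(a) states: "The primary endpoint analysis will be conducted on the ITT population". That population "includes all study participants and the treatment group to which they were assigned (i.e., the intended treatment". It adds: "An ITT analysis will also be conducted for the secondary endpoints".

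Section 6(b) removes from the per-protocol set, among others, anyone who missed the planned dose or was given the wrong drug, and then labels the set as treated: "receiving the incorrect study drug, or not obtaining consent (i.e., as treated". The primary analysis is to be repeated on this set.

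Section 6(c), on the safety population, states: "Participants will be analyzed based on the intervention they receive".

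Section 7.2 says the regression will "model the mean differences in the range of motion as a function of the intervention received". The unadjusted model is to assess whether means in participants who "received Ketotifen Fumarate (2 mg or 5 mg) differed from those who received lactose placebo".

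In Table 2 the primary-endpoint row gives linear regression and names no treatment term. The ANCOVA rows list *Treatment group* as the independent variable without saying whether it is assigned or received. Section 7.4 analyses the imputed data with the Section 7.2 model.

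**The concern.** The SAP gives two grouping rules for the same endpoints. A programmer working from Section 6(a) would code the randomized arm. One working from Section 7.2 would code the arm received. Each could cite the plan.

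The conflict matters most for the primary endpoint, because the Section 7.2 paragraph is the only place where the treatment term of the primary model is described. The same wording carries into the multiple-imputation analysis. Grouping by treatment received gives up the protection of randomization in the comparison of each dose with placebo, and Section 6(a) was written to keep that protection. The SAP itself foresees that assigned and received treatment may differ, since Section 6(b) lists a missed planned dose and an incorrect drug as major deviations.

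**Working it through.** **Step 1. The rules side by side.**

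- Section 6(a), primary and secondary endpoints: assigned group, all participants.
- Section 7.2, range-of-motion model: intervention received.
- Section 6(c), safety population: intervention received, in nearly the same words as Section 7.2.
- Table 2, primary row: no treatment term. ANCOVA rows: *Treatment group*, not defined.
- Sections 7.1 and 7.3: summaries and subgroup analyses refer to the ITT population.

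Section 7.2 is therefore the one efficacy statement that conflicts with Section 6(a), and it does so in the words the SAP uses elsewhere for as-treated grouping.

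**Step 2. Who would be affected if Section 7.2 were followed literally.**

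- Randomized but never dosed: has an assigned arm but no arm received. Could be left without a group.
- Given the wrong drug or dose: the arm received differs from the arm assigned. Could be moved.
- Started and then stopped: has received the assigned drug. Not affected.

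**Step 3. Planning figures, for scale.** Inputs from Section 4: difference 10°, SD 25°, dropout 11%, 127 per arm (381 in total). The two-sided 0.05 level is stated for the first calculation. Section 4 states no power for the recalculation.

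- n per arm = 2 × (1.960 + z)² × 25² / 10² = 12.5 × (1.960 + z)².
- At 85% power, z = 1.036: 12.5 × 2.996² = 112.2, rounded up to 113. Then 113 / (1 − 0.11) = 127 per arm and 3 × 127 = 381, an exact match.
- At the 95% power stated for the first calculation: 163, inflated to 184 per arm (552), which does not match.

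So 85% is inferred, not stated. The contradiction does not rest on it. It only supplies 113 evaluable participants per arm for the illustration.

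**Step 4. Size under an assumed share never dosed.** The SAP gives no such share. Let f be the share in each arm, and assume that never-dosed participants get no drug effect and otherwise have the same prognosis.

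- By assigned arm: expected difference 10 × (1 − f)°, with 113 per arm.
- With never-dosed participants left out: expected difference 10°, with 113 × (1 − f) per arm.
- Gap: 10 × f°.

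| f | Of 381 | Assigned | Left out | Gap | Power, assigned | Power, left out |
|---|---|---|---|---|---|---|
| 1% | 4 | 9.9° | 10° | 0.1° | 84.5% | 84.9% |
| 2% | 8 | 9.8° | 10° | 0.2° | 83.8% | 84.5% |
| 5% | 19 | 9.5° | 10° | 0.5° | 81.5% | 83.4% |
| 10% | 38 | 9.0° | 10° | 1.0° | 77.2% | 81.4% |

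Example at 5%: the standard error by assigned arm is 25 × √(2/113) = 3.326°, and 9.5 / 3.326 − 1.960 = 0.90, which gives 81.5%.

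**The case against.** The best defence is that Section 6 exists to fix the analysis sets, names these endpoints, and states the assigned-group rule, while Section 7.2 describes the form of the model. Section 4 also uses *received* loosely for the arm, and the second sentence of Section 7.2 is grammatically broken. Both suggest careless drafting, not a chosen as-treated analysis. This shows that intent was probably ITT. It does not remove the conflict, because Section 6(c) gives the same words an as-treated meaning and nothing in Table 2 defines the term.

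Three stronger readings are tempting, and the document does not support them.

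- *Participants will be dropped or moved.* Section 7.2 has no exclusion or reassignment rule. This follows only if its phrase is taken literally and allowed to override Section 6(a).
- *Tolerability would bias the comparison, perhaps by as much as 2°.* A shift of that size needs, for example, 10% of an active arm to be non-starters whose motion is 20° worse, with no matching difference in placebo (0.10 × 20° = 2.0°). Someone who has taken no capsule cannot have stopped for tolerability, and Section 3.2 makes the capsules indistinguishable, so never starting should not depend on arm. Someone who starts and stops keeps the same received arm.
- *The per-protocol result would change with the reading.* The exclusions in Section 6(b) already remove those with a missed planned dose or an incorrect drug. Assigned and received arm then coincide for everyone left, and only the label is wrong.

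**Conclusion.** Section 7.2 is wrong as written: followed literally, it gives a primary analysis that is not the ITT analysis required by Section 6(a), and Section 7.4 carries that into the imputed data.

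The numerical effect is unknown, because the SAP states no rate of non-dosing or misdosing, and it is probably small. Under the assumptions above, the literal reading targets a difference larger by 0.5° at 5% never dosed and 1.0° at 10%, and under those assumptions there is no gap if the drug has no effect. Only actual dosing errors would move anyone between arms. The case for correcting it is that a confirmatory plan should define its primary treatment variable once and without ambiguity, not that a large bias has been shown.

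**What to change.** - In Section 7.2, state that the model is a function of the randomized treatment group (2 mg, 5 mg or placebo), regardless of study drug taken.
- Rewrite the following sentence in full, so that it compares mean range of motion in participants randomized to each ketotifen dose with that in participants randomized to placebo. Swapping single words would leave the sentence ungrammatical.
- In Table 2, define *Treatment group* as the randomized arm for all efficacy endpoints, and name it in the primary-endpoint row.
- Keep grouping by treatment received for the safety population only, as Section 6(c) already does.
- As a minor tidy-up, delete the as-treated label in Section 6(b).

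These are wording changes. They need no new data and no change to the sample size, and they should be made before unblinding.
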